## 9.0 DATA AND SPECIMENS

### a) Handling of Data and Specimens

#### ALERT Immunization Information System (IIS) Abstraction

We will extract clinic-level data through ALERT IIS – via our collaboration with OIP – to investigate how the intervention we are testing affects patient outcomes (increases in HPV vaccine series completion) and practice outcomes (reductions in missed opportunities to vaccinate). These data will be used to determine how clinic rates of delivering HPV vaccination series changed throughout the study. We will identify established male and female patients in each practice who are between the ages of 11-17 years. Information on number of visits and dates of services for each patient in the practice during the study years outlined in our application will be captured.

### b) Sharing of Results with Subjects

Practices will receive their HPV vaccination rate data via ALERT IIS.

### **c) Data and Specimen Banking**

Not Applicable.

## **10.0 RISKS TO SUBJECTS**

Risks associated with this project are expected to be minimal; loss of confidentiality is the greatest potential risk. The surveys and assessments, mentioned above, pose minimal risk to practice members because the instruments contain minimal personal information. It is possible that someone in the practice could use information about a respondent's role (e.g., Office Manager) to identify that person and his or her responses. For this reason, our study team collects these data personally, and the data we collect is kept completely confidential and only used by the study team. If data is reported to practices, we report these data in aggregate so that it is not possible to link an individual to his or her responses. The risk of loss of confidentiality for patients/parents is higher because the survey for these individuals contains more sensitive information about HPV knowledge and attitudes regarding vaccination.

All data entered or sent to the study offices will be handled in a highly confidential manner consistent with the high standards established at OHSU and ORPRN. All employees at OHSU and ORPRN are required to sign a confidentiality statement and abide by standards of confidentiality and data security outlined in a manual developed for this purpose. A unique encrypted identifier will replace names on all study instruments and documents, including field notes and interview transcripts, and in a master database that will hold all study data. Data presented in all presentations and publications will not be associated with the name of any participating person or practice. All computer systems at OHSU and ORPRN are protected from possible external access using network security systems. Only study researchers and staff will have access to the data.

We will use industry standard Secure Sockets Layer (SSL) technology with server and client certificates to insure the confidentiality of data use and any data transfer.

## **11.0 POTENTIAL BENEFITS TO SUBJECTS**

### Potential Benefits of the Proposed Research to the Subjects and Others

The study may contribute long-term benefits of new scientific knowledge about providing HPV vaccinations to male and female patients aged 11-17 years. The participants will not directly benefit from their participation. The benefits of improving cancer risk reduction and vaccine delivery processes far outweigh the remote possibility of a breach in confidentiality.

### Importance of Knowledge to be Gained

The information gained from this study may provide critical information on how to reduce the burden of cancer in morbidity and mortality. The findings from this research may be useful to other areas of vaccine research. Additionally, this study will help us understand how to improve QI within rural primary care practices, and it will help determine the relationship between community-based organizations and primary care practices.

## 12.0 TIMELINE & MILESTONES

[figure not shown]

Figure 2. Overall Project Timeline

Figure 3. Aim 1 Timeline (below)

### RAVE Aim 1 Timeline

	Jun	Jul	Aug	Sept	Oct	Nov	Dec	Jan	Feb	Mar	April
Planning	X	X	X								
Tool refinement		X	X								
Clinic ranking			X								
Recruitment				X	X	X	X	X	X	X	
Obs. visits completed (20)*				1	3	3	2	2	2	4	3
Analysis					X	X	X	X	X	X	X
Aim 2 Instrument refinement							X	X	X	X	X
Dissemination								X	X	X	X

\* We will monitor for saturation, which may occur after 12-15 visits.

## 13.0 BIO-STATISTICAL CONSIDERATIONS

Our proposed stepped-wedge cluster randomized trial (78) will evaluate the impact of the proposed intervention on HPV outcomes in 40 primary care practices (Aim II). We will specifically test two hypotheses: 2a) More patients will have initiated and completed the HPV vaccine series in intervention practices compared to control practices, and 2b) Practices receiving the intervention will have lower rates of missed opportunities to vaccinate compared to control practices. The primary outcome variables will include receipt rate of the initial (age 11-12 years) and full series of HPV vaccines and a reduction in the rates of missed opportunities to vaccinate among males and females aged 11-17 years. We will conduct block randomization of practices in five waves every six months. Outcomes will be measured every three months in all clusters at every period, so that each cluster provides data points in both the control and intervention conditions. Practices in each wave will be stratified based on designation of pediatric or family medicine clinic to balance pediatric/family medicine clinics at each wave. Outcome data collection will be collected from ALERT IIS beginning in quarter four of the study and up to 17, for 14 longitudinal data collection points per practice. [name], who has no contact with the study practices, will perform the randomization for all practices prior to the start of the first intervention wave. Randomized assignment will not be revealed to practices until their cluster begins the study.

The primary goal of Aim II is to establish whether the intervention is effective and the degree to which it is accomplishing its goals. Our outcome evaluation includes a rigorous research design so we may attribute positive findings to the intervention and not to existing threats to internal validity. To compare the effect of the intervention with usual care on HPV outcome measures in the context of a stepped-wedge design, we will utilize Generalized Linear Mixed Models (GLMMs) (79). In particular, to assess the intervention effect, we will use a Poisson model with random effects for practice. The general model is as follows:

$$(1) \log(Y_{it}|b_i) = \beta_0 + \beta_1 t + \beta_2 I_{it} + \beta_3 I_{it}(t - s_i) + \beta_4 Z_i + b_i + \log(E_{it})$$

where  $Y_{it}$  is the number of patients in practice  $i$  who had HPV completion during period  $t$  for  $t \in (0, 1, \dots, 13)$ . Data is collected every three months (i.e., quarterly), and  $t = 0$  is the baseline quarter. Additionally,  $I_{it}$  is an indicator variable where  $I_{it} = 1$  if practice  $i$  has been assigned to the intervention at period  $t$ , and  $I_{it} = 0$  otherwise. Term  $s_i$  is the period when the intervention begins for practice  $i$ . The practice-level term to denote a family medicine or pediatric practice is denoted by  $Z_i$  where  $Z_i = 1$  if practice  $i$  is a family medicine practice and  $Z_i = 0$  if pediatric practice.  $E_{it}$  is the number of patients in the practice  $i$  who were eligible to be counted during period  $t$  and the  $\log(E_{it})$  term is considered the 'offset' in the Poisson regression model. The term  $b_i$  denotes a random effect term for practice  $i$  with mean 0 and variance  $\sigma_b^2$ . The estimation via model (1) takes into account the general time trend, and allows for the intervention effect to grow over time following intervention implementation. Model (1) estimates the intervention effect with the within site difference between HPV completion rates pre- and post-intervention, averaging across practices and accounting for possible secular trends which might confound with the timing of the intervention implementation. In model (1),  $\beta_0$  is the (log of) average pre-intervention HPV completion rate for pediatric practices (i.e.,  $Z_i = 0$ ) with the random effect set to 0.  $\beta_1$  is the effect of the general time trend of the HPV completion rate without the intervention.  $\beta_2$  represents the intervention effect that appears in the first time period of the intervention.  $\beta_3$  represents the added intervention effect that accrues over time following intervention implementation. Model (1) will also apply for outcome of HPV initiation, completion, and rates of missed opportunities to vaccinate by replacing  $Y_{it}$  and  $E_{it}$  with the appropriate numerator and denominator. Hypothesis tests will be two-sided, with type I error set to 0.05. Because statistical tests are specified a priori and our proposed outcome measures are highly related, we will follow recommendations to report p-values rather than adjust for multiple comparisons (80, 81). Goodness of fit statistics and model fitting diagnostics will be used to assess for influential points and over-dispersion and to evaluate alternative model specifications.

**Power Calculations:** We assess the power to detect effects that are clinically meaningful and realistic. For this calculation, we assess the power to detect at least 80% power of a 2-sided significance test with  $\alpha = 0.05$ . We are interested in comparing the rate of HPV completion in the sixth quarter after intervention with HPV completion rate at baseline. Given the following conditions: 1) Pre-specified total sample size of 40 practices; 2) Design (stepped-wedge with five cohorts of eight practices starting six months apart); 3) Two-sided significance level of 0.05; 4) Starting practice-level HPV completion of 24% as described above; 5) Intra-cluster correlation (ICC) of patients within practices of 0.08 (82, 83), we will have at least 80% power to detect a minimum of 19.4% difference in the absolute change (increasing from 24.0% to 43.4%). If we are successful at retaining all 45 practices that will be recruited, we will have at least 80% power to detect a 18.1% difference in absolute change. These estimates assume a conservative ICC of 0.08. As most studies show an  $ICC < 0.001$  (84), the proposed study will have sufficient power to detect differences of health policy importance. Estimates of parameters for these power

calculations were obtained from model (1) and the most recent, up-to-date OIP dataset. These power calculations estimate the minimum numbers needed to detect minimum changes.

Analysis Considerations: If we find significant practice differences between cohorts, we will utilize propensity score weighting methods to reduce the observed bias, help minimize external threats to the validity of results, and adjust for imbalances (85, 86). Additionally, model (1) can accommodate missing data resulting from practice attrition. We will explore model missingness by including relevant variables in the analysis as covariates (87, 88). If non-trivial levels of missing data are observed, we will use methods such as multiple imputation to include these practices in analyses (87). We will conduct a sensitivity analysis comparing parameter values for models using completers only, all practices without multiple imputation, and all practices with multiple imputation, to understand any biases introduced by differential attrition or missing not at random (88). Our project has control, intervention, and follow-up periods in all seasons, which will allow us to detect and account for the potential effect of seasonality on the receipt of indicated adolescent vaccines.

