Studies on medical practice barriers indicate that inadequate reimbursement (68%) and burden of determining insurance coverage (66%) all inhibit primary care practices from stocking the vaccine and providing it to adolescents (29, 30). Practices not providing the vaccine reported more concerns about HPV vaccine provision than practices providing it (n=71 practices: 6.0 vs. 4.5 concerns, p < 0.05) (29). Other barriers include parents deciding to delay rather than refuse vaccination. When this occurs, clinicians are hesitant to discuss the topic, while teens consider themselves passive in the decision-making process (31a).

To overcome these barriers, clinicians either present the HPV vaccine as routine or as optional, while highlighting risks and benefits (31). Additional studies have examined why clinicians do not follow clinical practice guidelines (31b). One systematic review of 76 published studies (31) identified seven common barriers, including lack of awareness, familiarity with details, lack of agreement with guidelines, issues related to self-efficacy (ability to reach goals) (31), outcome expectancy (belief that given behaviors will lead to certain outcomes) (32), ability to overcome practice inertia, and external barriers – such as health insurance coverage (33). Importantly, barriers in one setting are not generalizable to other settings (34). Improving primary care practices’ rates of HPV vaccinations will require a tailored approach.

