### 3.0 STUDY DESIGN/METHODOLOGY

**Aim I: Primary Care and Community-based Organizations:** Conduct a baseline assessment of how primary care practices, public health programs, and community-based organizations are initially addressing initiation and completion of the HPV vaccine series.

We have already determined HPV vaccination rates in 53 rural primary care practices (available from the Oregon Immunization Program – OIP), which has helped us identify “hot spots” for intervention research. We will conduct a baseline assessment in 20 of these practices using direct observation of workflows and validated measures of team-based care effectiveness and practice-level knowledge of HPV and current HPV vaccine recommendations. This will assist us in developing tailored intervention approaches for busy rural primary care practices and enable us to assess which practice characteristics affect delivery of the full HPV series. We will also conduct an in-depth assessment of activities undertaken in rural Oregon communities to inform the public about cancer risks and HPV vaccines.

**Aim II: Primary Care:** Implement and test, using a stepped-wedge cluster randomized trial design, the effectiveness of a multi-component primary care practice-based intervention on initiation of and completion of the HPV vaccine series as well as reduction in rates of missed opportunities to vaccinate.

The intervention will be conducted in 40 primary care practices we plan to enroll and will involve: 1) practice facilitation to engage clinics in a practice-wide planning process to redesign patient care and communication strategies to optimize HPV vaccine completion; 2) workflow mapping adapted to practice context to support HPV vaccine delivery; 3) a practice improvement model designed to firmly establish reminder and recall systems and standing orders; and 4) education for patients and parents that underscores HPV vaccination is safe, effective, and an important approach for reducing cancer risk. We will additionally explore uptake of the intervention in terms of implementation timing and component features in high- and low-functioning practices to determine which practice characteristics affect delivery of the full HPV series.

**Aim III: Community Organizations:** To explore the extent to which an evidence-based social marketing campaign, implemented in partnership with participating practices, will increase HPV vaccine demand.

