### 4.0 STUDY POPULATION

Rural adolescents aged 11-17 years, along with their parents, will be included in this study. In addition, rural family physicians and pediatricians and members of their clinical practices will be active participants and will uniquely partner with community-based organizations to undertake comprehensive communication, education, and social messaging approaches to address inequities in a much understudied population, rural America. Members of community-based organizations who partner with practice members to implement a social media campaign will also be participating.

The numbers below reflect the anticipated recruitment of 11-17 year old subjects in rural Oregon, according to 2015 U.S. Census Bureau Data from Oregon on gender, race, and

**Table 1. Total Planned Enrollment:** ethnicity status.

TARGETED/PLANNED ENROLLMENT: Number of Subjects			
Ethnic Category	Sex/Gender		
	Females	Males	Total
Hispanic or Latino	1,384	1,355	2,739
Not Hispanic or Latino	9,511	9,324	18,835
Ethnic Category: Total of All Subjects *	10,895	10,679	21,574
Racial Categories			
American Indian/Alaska Native	196	192	388
Asian	479	470	949
Native Hawaiian or Other Pacific Islander	44	43	87
Black or African American	228	224	452
White	9,948	9,750	19,698
Racial Categories: Total of All Subjects *	10,895	10,679	21,574

\* The “Ethnic Category: Total of All Subjects” must be equal to the “Racial Categories: Total of All Subjects.”

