**Table 2. Measures and Methods According to Solberg Model Constructs**

Aim I: Data Collection Methods & Timing	Measures	Solberg Model Constructs
Pre-Site Visit Phone Interviews – once at Baseline	
 
1. Staffing structure
 
2. Presence of QI team
 
3. EHR
 
	Priority
Formal Site Visit – once at Baseline	Baseline workflows; baseline patient data collection: eligible patient population, patient demographics, and other characteristics of the patient population; baseline immunization rates; baseline community education data: existing education programs and efforts, existing partnerships	Content
Practice Intake Survey (PS) – once at Baseline	
 
1. Ownership
 
2. Presence of a designated QI team
 
3. Relationship with community groups with regard to public health (and description, quantity)
 
4. Percentage of minor patients
 
5. Total patient visits in past week
 
6. Patient demographics (Race & Ethnicity)
 
	Priority

ALERT IIS – once at Baseline	1. Vaccine initiation rates for children ages 11-12 2. Vaccine completion rates for children ages 13-17 3. Insurance status	Priority
Community Partner Survey – once at baseline	Knowledge and perceptions of HPV vaccinations; relationship between HPV and cancer; perceived utility of a social marketing campaign on HPV vaccination, community health, and cancer rates	Priority Content
Aim II: Data Collection Methods & Timing	Measures	Solberg Model Constructs
Practice Survey (PS) – annually	Practice & practice’s patient demographics, practice change, payer mix, revenue & payments, HPV vaccine priority	Priority
	Internal structure & strategies for improving HPV vaccine rates, external reporting, registries & clinical guideline availability	Capability
Staff Member Survey (SMS) – annually	Staff member demographics, adaptive reserve, patient needs, clinician and staff satisfaction and burnout, staff motivation, staff turnover, practice leadership, practice cohesion and rewards	Priority
	Practice readiness to change	Capability
ALERT IIS – every six months (or more, TBD)	1. Vaccine initiation rates for children ages 11-12 2. Vaccine completion rates for children ages 13-17 3. Insurance status	Priority
Quality Improvement Change Questionnaire (QICA) – every six months	Engaged Leadership	Priority

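### Model (1) has only a random practice intercept and no pre-specified cluster-robust variance, so its two-sided 0.05 level is not protected if practice trends or effects differ

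*Combined protocol and SAP*

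**What the plan says.** Section 13.0 sets out one model for initiation, completion and missed opportunities: "to assess the intervention effect, we will use a Poisson model with random effects for practice". Equation (1) has a common linear time slope (beta1), an immediate intervention effect (beta2), a growth term (beta3), practice type and an offset. Although the sentence speaks of random effects in the plural, only b_i is defined, and it "denotes a random effect term for practice" with a single variance. The error rate is fixed: "Hypothesis tests will be two-sided, with type I error set to 0.05".

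The one safeguard is this sentence: "Goodness of fit statistics and model fitting diagnostics will be used to assess for influential points and over-dispersion and to evaluate alternative model specifications". It names no alternative model and no criterion for switching. The rest of Section 13.0 covers propensity weighting, missing data and seasonality, not variance estimation.

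Elsewhere the protocol expects practices to differ. Section 1.0 says that improving vaccination rates "will require a tailored approach". Under Aim II, Section 3.0 will "explore uptake of the intervention in terms of implementation timing and component features in high- and low-functioning practices".

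**The concern.** Given b_i, the model treats a practice's 14 quarterly counts as independent Poisson observations around a trend and an intervention effect shared by all 40 practices. The intercept absorbs differences in level only. In a stepped wedge, beta2 and beta3 come mainly from change within practices over time. Differences between practices in slope or response therefore fall directly on these estimates, while the model-based standard errors ignore them.

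At stake is whether a p-value below 0.05 for a primary outcome has its stated meaning, and whether any 95% interval reported with it has its stated coverage.

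**Working it through.** **Inputs from the documents.** 40 practices, five waves of eight six months apart, 14 quarters, 24% starting completion, ICC 0.08 and two-sided 0.05 (all Section 13.0). Table 1 in Section 4.0 gives 21,574 as the "anticipated recruitment of 11-17 year old subjects in rural Oregon". Table 2 lists "Vaccine completion rates for children ages 13-17" and initiation rates for ages 11-12.

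**Assumptions.**
- Patients per practice: 21,574/40 = 539. With the seven years of age spread evenly, 539 × 5/7 = 385 are aged 13-17 (completion) and 539 × 2/7 = 154 are aged 11-12 (initiation).
- Waves start at t = 2, 4, 6, 8, 10. The common trend is 0.01 log units per quarter.
- Intercept SD from the ICC: variance of practice rates 0.08 × 0.24 × 0.76 = 0.0146, squared CV 0.0146/0.24² = 0.253, log SD √ln(1.253) = 0.475.
- Practice-specific log-trend SD of 0, 0.01 or 0.02 per quarter. For scale only: the national rise in male completion quoted in Section 1.0, 21.6% to 28.1% in a year, is ln(28.1/21.6)/4 = 0.066 per quarter.
- Contrast: beta2 + 5·beta3, the sixth intervention quarter, which is the comparison used for power.

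**The plan's own figure.** With Poisson counts, no heterogeneity and 539 patients, fitting model (1) by adaptive quadrature (1,000 trials, Monte Carlo SE about 0.7 points) rejects 4.6% (beta2), 5.4% (beta3), 6.7% (sixth quarter) and 5.1% (joint). The level is close to 0.05 when the model is true.

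**False positives for the sixth-quarter contrast, true effect zero.** These come from 1,500 to 2,000 trials per scenario, with model (1) fitted by penalised quasi-likelihood. Completion is read as the share of eligible adolescents who have completed (24%):

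| Patients per practice | SD 0 | SD 0.01 | SD 0.02 |
|---|---|---|---|
| 154 | 1.5-1.7% | 5% | 17% |
| 385 | 1.5-1.7% | 11% | 33% |
| 539 | not run | 16% | 40% |

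The SD 0 column is conservative because the variance of a proportion at 24% is 0.76 of the Poisson variance.

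**Check from the standard errors** (385 patients). The rejection rate is about 2[1 − Φ(1.96 × model SE / true SD)], with the robust SE standing in for the true SD. At SD 0.02: 1.96 × 0.026/0.052 = 0.98, giving 33%. At SD 0: 1.96 × 0.026/0.022 = 2.32, giving 2%. Both agree with the simulation.

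**Other readings and settings, 385 patients.**
- Completed adolescents carried over between quarters (5% turnover assumed): 2%, 11% and 33% at SD 0, 0.01 and 0.02.
- Incident reading, completions within the quarter (3% assumed): 5%, 5% and 9%.
- Effects that differ with no practice harmed (log effect uniform 0 to 0.4): a nominal 95% interval misses the mean effect in 21% (beta2) and 17% (sixth quarter). At 154 patients it misses in 10% and 6%, and on the incident reading in 7% and 5.5%.
- SD 0.02 with the first wave at t = 1: 28%. SD 0.02 with unequal practice sizes (CV 0.6): 39%.

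**Does the dispersion check catch it?** Mean dispersion was 1.00 at 154 patients with SD 0.02 (17% rejected) and 0.97 at 539 with SD 0.01 (16% rejected). With carry-over it was 0.22, 0.38 and 0.85. Scaling the standard errors by dispersion still left 7.5 to 27%.

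**Agreement between methods.** The quadrature fit (539 patients, Poisson counts, first wave at t = 1) gave 18% and 42% at SD 0.01 and 0.02. A conditional Poisson analysis with practice effects removed (385 patients, 600 trials) gave 1.3%, 14.5% and 30.7% at SD 0, 0.01 and 0.02. For effects uniform 0 to 0.4 it gave interval misses of 21.7% (beta2) and 13.8% (sixth quarter).

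**With the remedy.** Mancl-DeRouen standard errors with t on 39 df gave 4.0 to 5.7% for the sixth-quarter contrast in every scenario of the main simulation, and 3.5 to 6.7% in the conditional Poisson check.

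**The case against.** The strongest reply is that the plan also promises to evaluate alternative specifications, and that this could work. In 400 trials per scenario, a likelihood-ratio test of a random practice slope against model (1) detected the slope in 99 to 100% of trials in four settings: 385 patients with SD 0.01 and 0.02, 154 with SD 0.02, and 539 with SD 0.01. After choosing the model by that test, false positives were 2.0 to 3.2%. Where detection was weaker (55% at 154 patients, SD 0.01), little inflation remained to be missed (4.8%). This shows that a named slope comparison would help. The plan names neither that comparison nor a rule for acting on it, so an analyst who follows the text need not run it.

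Other points stand as limits on size:
- The tailoring and uptake passages point to differing responses more than to differing underlying trends. The trend SDs have no source in the documents.
- If no practice responds, effect heterogeneity cannot inflate a null test. The uniform-effect scenario concerns interval coverage, and Section 13.0 does not mention intervals.
- The equation's definition of Y can be read as completions within the quarter, where inflation is small. The 24% in the power paragraph points to the cumulative share. The text leaves this open.
- The sixth-quarter contrast comes from the power paragraph and is not named as the test. At 385 patients, beta2 alone rejected 3.0% and 7.5% at SD 0.01 and 0.02, while beta3 rejected 18% and 43%.
- Practice sizes derive from a census-based enrolment table, and inflation grows with size.

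**Conclusion.** The concern holds and should be fixed before analysis. As written, model (1) with model-based standard errors keeps its 0.05 level only if practices share one trend and one response, and nothing pre-specified protects it otherwise. On the cumulative reading, modest trend differences (SD 0.01 to 0.02 per quarter) give false-positive rates of 5 to 40% for the sixth-quarter contrast, depending on practice size. On the incident reading the range is 5 to 9%, and with no extra variation at 24% the test is conservative.

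These sizes rest on assumed heterogeneity, practice sizes and wave starts. The missing protection does not: it is a matter of the text. The planned over-dispersion check is not a substitute, because under-dispersion of a proportion at 24% can mask the extra variation.

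**What to change.** Keep the fixed part of model (1). State in Section 13.0 that all primary tests and intervals use practice-clustered sandwich standard errors with a named small-sample correction (for example Mancl-DeRouen) and a t reference on about 39 df. The correction matters: a simpler K/(K − p) sandwich rejected up to 8.8% under strong heterogeneity.

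Report the random-intercept model-based results as a sensitivity analysis. A random practice slope or random intervention effect can be a second, named sensitivity model. In 300 trials at 385 patients and SD 0.02, the slope model rejected 2.7%.

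The cost is SAP wording and a few lines of code. Intervals widen only where heterogeneity exists: at 385 patients the SE of the sixth-quarter log ratio goes from 0.026 to 0.052 at SD 0.02, and from 0.026 to 0.022 with no extra variation. With 539 patients and the simpler sandwich, power for 24.0% to 43.4% stayed at 97% or more, even at trend SD 0.05 (200 runs per scenario).
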